 - Pain of procedure: To assess pain of procedure, we will use the 11 point Numeric Pain Rating Scale (NPRS). We expect that the patients receiving 10 injections will have less pain associated with the procedure. The patients will rate their level of pain immediately following the completion of bladder injections by selecting a whole number from 0 to 10 that represents their level of pain (0 is no pain at all and 10 is the most severe pain) during the procedure. This scale has been validated, and correlates similarly to other pain scales [7].
- Secondary endpoints: Secondary endpoints to be assessed will be efficacy, OAB symptoms (nocturia, urgency, and frequency), post void residual volume (PVR) at 2 weeks and 12 week post-procedure, disease specific bother, health related quality of life (HRQoL), the patient's perceptions of change, and adverse events as detailed below:
 - Efficacy: The reduction in mean urge incontinence episodes which will be calculated by averaging the amount of urge urinary incontinence episodes over 3 days as recorded in a bladder diary. Success will be defined as a greater than 50% reduction in urge incontinence episodes after intradetrusor Botox® based on 3-day bladder diaries collected at baseline and 12 weeks post-injection. This outcome measure is consistent with results reported in previous trials involving Botox® for overactive bladder [6].
 - Disease specific bother and HRQoL: To assess OAB symptoms other than incontinence and impact on quality of life, we will administer the Overactive Bladder Questionnaire Short Form (OABq-SF) at baseline, at 2 weeks, and at 12 weeks post-procedure. This is an abbreviated version of the Overactive Bladder Questionnaire (OABq) developed to evaluate the bother and health related quality of life for patients with overactive bladder. The OAB-SF contains 6 items to assess symptom bother and 13 items to assess HRQOL. This questionnaire is commonly used, and has been validated for use in clinical practice [8].
 - PVR at 2 weeks and 12 weeks: To measure PVR at 2 weeks and 12 weeks, we will use a bladder scanner which measures volume based on ultrasound. The provider may also chose to measure PVR by straight catheterization at his or her discretion.
 - Patient's Global Impression of Change (PGIC) scale: In order to help determine the clinical significance of change, we will utilize the PGIC scale [16] administered at 2 weeks and 12 weeks post-injection.

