Adverse events: Specific to intradetrusor injections of Botox®, the most common adverse events are urinary retention requiring intermittent catheterization (approximately 4%) [9] and urinary tract infections (approximately 15.5%-35%) [10]. Patients will be closely monitored for urinary tract infections as they will undergo urinanalysis and assessment of symptoms at their post-operative visits.

Methods and Measures

- Design:
 - This study is a randomized clinical trial to assess whether or not 10 injections of 100 units of intradetrusor Botox® toxin is perceived as less painful compared to 20 injections of 100 units of intradetrusor Botox® toxin for the treatment of refractory OAB. Refractory OAB is defined as persistent urinary frequency and urgency despite behavioral modifications, failing a trial of 2 medications (anticholinergics or beta 3 agonists), have a contraindication to the medications, or are unable to tolerate medications due to allergies or side effects.
 - The primary outcome will be assessed by the patient completing the pain of procedure questionnaire, the NPRS, to be completed by the patient immediately after the procedure. The patient will receive the questionnaire from the nurse or medical assistant after the provider has performed the procedure. We will then compare mean value of the NPRS for the 10 injection group to the 20 injection group.
 - Efficacy will be assessed by comparing study participant's reduction in urge urinary incontinence episodes based on a 3 day voiding diary to be shared by the participant at baseline and 12 weeks post-procedure. This diary is dispensed to all patients during their visit prior to procedure visit as a part of standard of care. If subjects demonstrate a 50% reduction in urge incontinence episodes on a 3-day bladder diary, they will be categorized as "treatment success" whereas those who do not will be categorized as "treatment failure." This dichotomous outcome will define efficacy as a secondary endpoint.

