After consenting to enrollment in the study, the patients will be scheduled for Botox® injections in the office. Randomization will be performed using random sequence number generation in blocks of 10 with randomization assignment concealed in sequentially numbered opaque envelopes. Randomization will be performed before the study startup by the coordinator using online available tool (sealed envelope). Envelopes with 50% carrying 10 injections instructions, and 50% carrying 20 injections instructions are prepared in advance, sealed, numbered 1 to 50, and stored in a locked cabinet at the Urology clinic at [name]. Three envelopes will be carried to the Greensboro Wake Health System during coordinator's scheduled clinic days. And then coordinator will bring those packets back to the [name] Urology clinic on a regular base. On the day of the procedure, the provider will select the next numbered envelope that will contain the randomization assignment for the number of injections. Subjects will be blinded to the randomization result. All patients will undergo a urinalysis prior to the procedure. If there is concern for an acute, untreated urinary tract infection, the patient does not undergo the procedure, and is treated with antibiotics while a urine culture is sent. All participants will be given preoperative antibiotics (except aminoglycosides). 100 units of Botox® will be combined with 20 cc saline for the purposes of 20 injections, or 100 units of Botox® will be combined with 10 cc of sterile saline for the purpose of 10 injections. Lidocaine Jelly locally. And the bladder will be instilled with 30ml of Marcaine and 5ml of NaHCo3 solution through a catheter for at least 15 minutes prior to the procedure. Cystoscopy with either a rigid or flexible cystoscope (per surgeon preference) will be performed using sterile technique. The Botox® will be injected in a grid like pattern avoiding the trigone as seen below. Study patients do not know the number of injections received in the bladder. There are two providers in the room for each procedure. Injection counting will be verbalized as Injection 1, Injection 2... to up to Injection 20 by non-injecting provider. A patient and a provider who is injecting will hear total of 20 counts. Providers will know the randomization prior to procedure, and a decision will be cleared between two providers whether to account pseudo injection at odd or even number for patients receiving 10 injections. A patient randomized to 10 injections will receive 10 injections at alternate count. All patients will be informed in advance about the procedure at the time of consenting. The patient will be allowed to void on her own postprocedure. Immediately after the procedure, the patient will receive a questionnaire to rate the pain of procedure using the numeric pain scale. The patient will then be discharged to home. Figure 1: Diagram showing sites of injections for patients undergoing 10 injections of 100 units of Botox®.

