- Exclusion Criteria:
 - 1. Male gender
 - 2. Neurological conditions (Examples: Cerebral vascular accident within 6 months prior to treatment, Parkinson's disease, Multiple Sclerosis, and Spina Bifida).
 - 3. Acute urinary tract infection
 - 4. Treatment with Botox® toxin for other conditions
 - 5. Allergy to Botox® toxin
 - 6. Hematuria that has not been worked up
 - 7. Known bladder malignancy

- 8. Previous history of bladder augmentation
- 9. Currently pregnant (with no plans to become pregnant within 6 months of enrollment) or breastfeeding
- 10. Currently taking aminoglycoside antibiotics
- 11.PVR >150 cc (measured by bladder scan or by catheterization) prior to enrollment
- 12. History of bladder pain syndrome.
- Sample Size:
 - This study is unique as there are no previous trials assessing pain of procedure associated with intravesical administration of bladder Botox. To calculate sample size in the study, we will assume an effect of size of 1. We expect that patients receiving 20 injections will be within the moderate pain range (between 5 to 7 on the NPR scale). Therefor we will assume a mean NPR rating for patients receiving 20 injections would be 6 with a standard deviation of 2. Patients receiving 10 injections will be expected to have less pain and be in the mild pain range (from 1 to 4 on the NPR scale). Based on this, we would need 16 patients in each group. Accounting for a 20% drop out rate, we would need to accrue 20 patients in each group.

• Statistical Analysis:

- 1. Primary endpoint: Each patient will be asked to rate her pain level of procedure by completing the NPRS immediately after her procedure. The mean NPRS score of each group (10 injections vs 20 injections) will be calculated and compared using a paired T test.
- 2. Secondary endpoints

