 - Each patient's mean number of urge urinary incontinence episodes will be calculated by averaging the number of urge urinary incontinence episodes collected over 3 days as recorded on a bladder diary. This will be calculated pre-intervention at baseline and at 12 weeks. As previously described, "treatment success" is defined achieving greater than 50% reduction in the number of urge urinary incontinence episodes at 12 weeks after treatment with Botox®. A "treatment failure" will be defined as achieving less than 50% reduction in the number of urge urinary incontinence episodes at 12 weeks after treatment with Botox®. A "treatment failure" will be defined as achieving less than 50% reduction in the number of urge urinary incontinence episodes at 12 weeks after treatment with Botox®. Our hypothesis is that there will be more significantly "treatment responders" in patients receiving 20 injections compared to 10 injections. To assess for clinical significance Chi square (X²) will be used.

- OABq-SF and PGIC collected from the group receiving 20 injections and the group receiving 10 injections. The mean will be calculated for each of the outcomes and for each of the groups. The result will be compared using paired t-test.
- We will compare the mean number of patients with urinary retention and UTIs in patients in both groups (those receiving 20 injections and those receiving 10 injections). To test for significance we will use the t-test.

Interventions and Interactions

- This study will use the FDA approved dose for refractory overactive bladder which is 100 units of onabotulinum toxin A (Botox®).
- Per surgeon preference, a flexible cystoscope or a rigid cystoscope will be used to inject the Botox® in the wall of the bladder.
- Injections will be in a grid-like fashion.
- We will use a 3 day bladder diary obtained from the International Urogynecological Association (IUGA) for baseline and 12 week follow up. (Appendix 1)
- Immediately after the treatment, patients will be asked to rate their pain using the Numeric Pain Scale. Please see appendix.
- Patients will be assessed for adverse events, symptom specific and global quality of life using the form in the appendix.
- All surveys will be handed to the patients by nursing. Patients will fill out the forms before seeing a physician.

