Official Title: A Randomized Clinical Trial of 100 Units of Intradetrusor Onabotulinum Toxin A for Refractory Overactive Bladder - Is 10 Injections Less Painful Than 20 Injections?

NCT04124939 Date: 7/31/23

Statistical Analysis - 10 vs 20 Botox Injections

Standard descriptive statistics were used to compare demographic and clinical characteristics. Frequency and percentages were reported for categorical data. Chi-square and fisher exact test for categorical variables and student t-test or Mann-Whitney U test for continuous variables were used to assess significant differences between the groups. Statistical analysis was performed on R Software.

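### The primary pain comparison is planned as a paired t-test on two independently randomised arms, and the SAP neither withdraws it nor names a test for the pain score

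*Protocol*

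**What the plan says.** **Protocol, Statistical Analysis, item 1 (primary endpoint):** "The mean NPRS score of each group (10 injections vs 20 injections) will be calculated and compared using a paired T test".

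**Protocol, Methods and Measures, Design:** the same comparison is described without any pairing: "We will then compare mean value of the NPRS for the 10 injection group to the 20 injection group".

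**Allocation and measurement (same section):** "Randomization will be performed using random sequence number generation in blocks of 10". On pain: "Immediately after the procedure, the patient will receive a questionnaire to rate the pain of procedure using the numeric pain scale". The Calendar of Events lists the pain scale on the procedure day only.

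**Protocol, Statistical Analysis, item 2:** for OABq-SF and PGIC a mean is calculated for each group, and then "The result will be compared using paired t-test". For PGIC, the Objectives say "we will utilize the PGIC scale [16] administered at 2 weeks and 12 weeks post-injection", so it has no baseline value.

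**SAP:** after an opening sentence about demographic and clinical characteristics, "student t-test or Mann-Whitney U test for continuous variables were used to assess significant differences between the groups". The pain score, the primary endpoint and the paired test are not mentioned.

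**Protocol, Sample Size:** with an effect size of 1, a mean of 6 and an SD of 2 for 20 injections, "Based on this, we would need 16 patients in each group", raised to 20 for 20% dropout. No alpha, power or sidedness is stated.

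**The concern.** A paired t-test analyses differences within defined pairs. Here a pair could come from only two sources, and the design supplies neither. One is two scores from the same woman, but she gives one. The other is matching women across arms, but none is described. Randomising in blocks of 10 balances numbers between arms and does not link any woman in one arm to a particular woman in the other.

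An analyst who follows the protocol literally must line up unrelated women in some order, and the p-value depends on that order. The arms must also be of equal size, or scores have to be dropped by a rule that is not given.

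The SAP does not clearly settle the matter. Read literally, the two documents leave three candidate tests for the primary endpoint: paired t, Student's t and Mann-Whitney. What is at stake is whether the headline p-value of a trial of about 40 women is determined by its data and its documents, or also by an unrecorded choice.

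**Working it through.** **Inputs.** From Sample Size: effect size 1, mean 6 and SD 2 with 20 injections, 16 evaluable per arm, 20% dropout. Effect size 1 × SD 2 gives a difference of 2 points, so a mean of 4 with 10 injections. Assumed, because the documents do not say: two-sided alpha 0.05 and, for the sample size, 80% power.

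**1. The plan's own sample size.** For two independent groups, by normal approximation:

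n = 2 × (1.960 + 0.842)² × SD² / difference² = 2 × 7.85 × 4 / 4 = 15.7, so 16 per arm; 16 / 0.80 = 20.

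This reproduces both stated figures with an unpaired formula. A paired test with a standardised within-pair difference of 1 would need 10 pairs at the same settings. That points to an unpaired calculation but does not prove it, since a paired formula also gives 16 at 5% alpha with 95% power, or at 1% alpha with 80% power.

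**2. Power under arbitrary pairing.** With unrelated women the correlation is 0, so the SD of a difference is √(4 + 4) = 2.83 and the standardised difference is 2 / 2.83 = 0.707. The noncentrality is the same for both tests:

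- unpaired: 1 × √(n/2)
- paired: 0.707 × √n = √(n/2)

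Only the degrees of freedom differ, 2n − 2 against n − 1. From the noncentral t distribution:

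| Per arm | Noncentrality | df unpaired / paired | Power unpaired | Power paired |
|---|---|---|---|---|
| 16 | 2.83 | 30 / 15 | 78.1% | 75.3% |
| 20 | 3.16 | 38 / 19 | 86.9% | 85.1% |

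The loss is 2.8 and 1.8 percentage points.

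**3. Dependence on the pairing.** Simulated trials, means 4 and 6, SD 2, normal scores rounded and limited to 0–10, 200 random pairings of each data set (3,000 and 10,000 trials per setting, separate seeds):

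| | 16 per arm | 20 per arm |
|---|---|---|
| One arbitrary pairing gives a different 5% verdict from the unpaired t-test | 7.0% | 4.3% |
| At least 10% of pairings fall on the minority side of 5% | 21–22% | 14–15% |
| Any of the 200 pairings changes the verdict | 38–39% | 26–27% |

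In the typical trial the verdict does not move: at 16 per arm the median 2.5th to 97.5th percentile range of p across pairings is 0.001 to 0.033.

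**4. Type I error (equal means, 10,000 trials).** One random pairing: 4.9–5.6%. Smaller p of Student's t and Mann-Whitney: 5.7–5.9%. Smallest of all three tests: 6.5–7.0%. Best of 10 pairings: 10–12%. The last two are ceilings on what the wording allows, not forecasts.

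**5. Equal arms.** If each of 20 women per arm independently had an 80% chance of a usable score, the arms would end equal in size with probability Σ P(k)² over the binomial(20, 0.8), about 16%. Pain is scored on the day, so real loss may be smaller. Any imbalance would still force scores to be discarded under a paired test.

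**The case against.** The strongest reply is that the SAP has already dealt with this. It is dated 7/31/23, its title asks whether 10 injections hurt less than 20, and it lists only unpaired tests for between-group comparisons of continuous variables. On that reading the pairing in the protocol is a slip of wording, which the Design section and the sample size both support. That is a fair account of what was probably intended. It does not close the point. The SAP opens on demographic and clinical characteristics, never names the pain score, and leaves Student's t or Mann-Whitney open with no rule. Even on the generous reading two primary tests remain.

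Three limits on the numbers stand:

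- The any-change figure of 38–39% grows with the number of pairings drawn: at 16 per arm, 23% with 10 pairings and 41% with 1,000. An analyst would run one pairing, so 7.0% and 4.3% are the figures to weigh.
- The protocol gives only a range of 1 to 4 for the 10-injection arm, and 4 is its top. It follows from the stated effect size and SD, but with a mean of 3 the any-change figure falls to about 7% at 16 per arm and 2% at 20, and disagreement for one pairing to about 1% or less.
- Nothing in the documents suggests that anyone would search over pairings.

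OABq-SF does have a baseline, so a within-patient comparison is possible there. The protocol's sentence, however, describes comparing group means.

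**Conclusion.** The concern holds. The primary test is wrong as written: it requires pairs that the design does not contain, and neither document states a single usable replacement. The same error recurs for OABq-SF and PGIC; for PGIC the pairing cannot mean change from baseline.

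The size is modest on average. Under effect size 1, SD 2 and an assumed two-sided 5% level, about 2 to 3 points of power are lost, type I error stays near 5%, and one arbitrary pairing disagrees with the unpaired test in about 7% of trials at 16 per arm and 4% at 20. These figures shrink if the true difference exceeds 2 points. The sample size is not overturned. The point is a must-fix because the primary analysis is not specified, not because a large bias is expected.

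**What to change.** 1. In both documents, name one primary test for NPRS: an unpaired two-sample t-test by randomised arm, with the mean difference and 95% CI. State whether Mann-Whitney is supportive, so that the choice is closed.
2. State alpha, sidedness and power for that test. Two-sided 5% is suggested; the hypothesis is directional and the documents are silent, so the choice must be explicit. On that basis 16 evaluable per arm gives 78% power, 17 gives 81% and 20 gives 87%.
3. Remove the pairing from the OABq-SF and PGIC comparisons. If a within-patient analysis of OABq-SF is wanted, describe it separately.
4. The SAP is written in the past tense. If the analysis has been run, rewording cannot make the test prespecified. Add a dated note of which test was used and that it departs from the protocol, and re-run the analysis if the paired test was used.
5. Minor: describe retention and UTI as proportions and use the SAP's categorical tests instead of the protocol's t-test.

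The cost is wording in two documents or, after analysis, a deviation note and perhaps a short re-run. No additional patients or data are needed.

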 - All eligible participants will be considered for the study. Patients will be counseled about the study in the office setting. Upon enrollment, patients will share a 3-day voiding diary. Diary is dispensed to all patients when they decide to undergo injection procedure. Disease specific bother and health related quality of life questionnaires will be completed following consenting. As per standard of care, urinalysis and post-void residual volume will be measurement. The only assessment in this list that is not part of standard clinical care are the questionnaires. If patients are on medications for

overactive bladder, they will be required to stop at least 3 weeks prior to undergoing the baseline 3 day voiding diary.

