
Figure 1: Diagram showing sites of injections for patients undergoing 10 injections of 100 units of Botox®.

[figure not shown]

Figure 2: Diagram showing sites of injections for patients undergoing 20 injections of 100 units of Botox®

- At two weeks, the patient will return to clinic for a standard office visit. She will have a post void residual checked using either a bladder scan or catheter, and a urinalysis (urine culture will be sent per clinic protocol). If a urine culture grows any bacteria, and the patient is symptomatic, she will be treated with culture specific antibiotics. She will then be asked about symptoms of a urinary tract infection, if they have been treated for a urinary tract infection, difficulty emptying the bladder, or required intermittent or an

indwelling Foley catheter since the Botox® therapy. Subjects will complete the PGI-C and the OAB-SF. The patient will be sent home with a 3-day bladder diary to complete just prior to the 12-week visit.

- At 12 weeks, the patient will return to clinic and her 3-day bladder diary will be reviewed. A post void residual volume will be checked using either a bladder scan or catheter, and a urinalysis will be sent per standard practice (urine culture will be sent per clinic protocol). If a urine culture grows any amount of bacteria and the patient is symptomatic, she will be treated with culture specific antibiotics. She will then be asked about symptoms of a urinary tract infection, if they have been treated for a urinary tract infection, difficulty emptying her bladder, or required intermittent or an indwelling Foley catheter since the Botox® therapy. She will again take the OABq-SF and PGIC.
- Setting:
 - This study will take place at two Urology clinic locations at Wake Forest Baptist Medical Center, [name] in Winston Salem, NC and [name] in Greensboro, NC.

Subjects Selection Criteria

- Inclusion criteria: Subjects must meet the following inclusion criteria in order to be eligible for the study
 - 1. Female gender
 - 2. At least 18 years of age
 - 3. Have already decided to undergo intradetrusor Botox® injections for treatment of refractory overactive bladder.
 - 4. Able and willing to learn clean intermittent catheterization (or care provider is willing and able to perform intermittent catheterization).
 - 5. Understands and is willing to undergo follow up and complete questionnaires as described in this protocol
 - 6. Able to give informed consent

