Appendix A. OAB-q SF and Scoring Manual OAB-q Short-Form

This questionnaire asks about how much you have been bothered by selected bladder symptoms during the past 4 weeks. Please place a ν or x in the box that best describes the extent to which you were bothered by each symptom during the past 4 weeks. There are no right or wrong answers. Please be sure to answer every question.

During the past 4 weeks, how bothered were you by	Not at all	A little bit	Some-what	Quite a bit	A great deal	A very great deal
1 An uncomfortable urge to urinate?	□ :	3			ņ	□ *
2 A sudden urge to urinate with little or no warning?			D,		Ļ	Ļ
3 Accidental loss of small amounts of urine?	-					
4 Nightlime uninglion?				— 1	_	
5 Waking up at night because you had to urinate?			□ ,		Ģ	Ļ
6. Urine loss associated with a strong desire to urinate?	-	□	D \$	□ ,		Ū

Neurourology and Urodynamics DOI 10.1002/nau

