Appendix 4: OAB Short Form for Bother to be completed at baseline, 2 weeks and 12 weeks.

Protocol version: 1 Page 17 of 21

262 Coyne et al.

The previous questions asked about your feelings about individual bladder symptoms. For the following questions, please think about your overall bladder symptoms in the past 4 weeks and how these symptoms have affected your life. Please answer each question about how often you have felt this way to the best of your ability. Please place a 🛩 or x in the box that best answers each question.

 Caused you to plan "escape zoutes" to restzooms in public places? 	None of the time	A little of the time	Some of the time	A good bit of the time	Most of the time	All of the tim
2. Made you feel like there is something wrong with you?			□ ↓		D,	Ď
3. Interfexed with your ability to get a good night's zest?				□		Ļ
4. Made you frustrated or annoyed about the amount of time you spend in the restroom?		_ 2			□	
 Made you avoid activities away from restrooms (i.e., walks, running, hiking)? 			D,			Ļ
6. Awakened you during sleep?			D	Ļ		Ļ
7. Caused you to decrease your physical activities (exercising, sports, etc.)?		Ļ	\Box_{i}		□ ;	
8. Caused you to have problems with your partner or spouse?			D			Ē
 Made you uncomfortable while traveling with others because of needing to stop for a sestnorm? 			۲ پ	Ļ	□ ,	Ļ
10. Affected your relationships with family and friends?				D ,		
11 Interfered with getting the amount of skeep you needed?		_			□	
12 Caused you embarrassment?			D,		 5	Ļ
13. Caused you to locate the closest restroom as soon as you arrive at a place you have never been?	П 1		ņ	Ļ	 ,	Ļ

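### The OABq-SF comparison between arms names no visit and leaves the collected baseline score unused, and week-2 answers partly describe time before the injection

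*Protocol*

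**What the plan says.** The Protocol (Objectives; Calendar of Events) collects the OABq-SF at baseline and again at weeks 2 and 12. It yields two scores, symptom bother and HRQoL. On the baseline form, the Design section says: "Disease specific bother and health related quality of life questionnaires will be completed following consenting".

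The analysis of OABq-SF and PGIC is one item under Statistical Analysis, Secondary endpoints: "The mean will be calculated for each of the outcomes and for each of the groups. The result will be compared using paired t-test". No visit, change score or covariate is named. The diary endpoint just above it does name its time points, baseline and 12 weeks.

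The SAP does not mention the OABq-SF. Its general rule is "student t-test or Mann-Whitney U test for continuous variables were used to assess significant differences between the groups".

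The bother items (Appendix 4) ask "how much you have been bothered by selected bladder symptoms during the past 4 weeks". The HRQoL items (Appendix 5) say "please think about your overall bladder symptoms in the past 4 weeks". For the first follow-up the Protocol says "At two weeks, the patient will return to clinic for a standard office visit", with no visit window.

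**The concern.** There are two separate issues.

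**Baseline and visit.** Two scores at two follow-up visits leave four candidate comparisons, and the plan does not say which one counts. Nor does it use the baseline score, which would reduce the unexplained variation in a trial of 16 to 20 patients per arm.

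**Week-2 recall.** A four-week question asked about two weeks after injection covers time before treatment. That time is common to both arms, so it pulls the difference between arms towards zero. A null week-2 result could then be misread as evidence that 10 and 20 injections work equally well.

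**Working it through.** **Can the paired test be read as baseline to follow-up?** The wording compares group means, and the same test is applied to PGIC, which has no baseline. The SAP also speaks of differences between groups. The primary NPRS, a single score per patient, likewise "will be calculated and compared using a paired T test". The within-patient reading therefore does not fit, and a within-arm change test would not compare 10 with 20 injections in any case.

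**The plan's own sample size.** The Protocol assumes an effect size of 1 for the NPRS. It states neither alpha nor power; I take two-sided 5% and 80%. Then n per arm = 2 × (1.96 + 0.84)² / 1² = 15.7, so 16, and 16 / (1 − 0.20) = 20. Both stated figures are reproduced. There is no sample-size figure for the OABq-SF.

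**Precision at week 12.** In SD units, the standard error of the difference between arms is √(2/n) unadjusted and √(2/n) × √(1 − r²) with ANCOVA, where r is the correlation of baseline with follow-up. With n = 16, √(2/16) = 0.354. The difference detectable with 80% power (normal approximation) is 2.80 × 0.354 = 0.99 SD unadjusted, and 0.94, 0.86 and 0.71 SD at r = 0.3, 0.5 and 0.7.

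Power was simulated with 100,000 trials per cell: normal scores, unit SD, effect on the post-injection state only, two-sided 5%, slope estimated. The true difference and r are assumptions, because the documents give neither.

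| Per arm | True difference | Unadjusted | ANCOVA r = 0.3 | r = 0.5 | r = 0.7 |
|---|---|---|---|---|---|
| 16 | 0.8 SD | 59% | 62% | 70% | 85% |
| 16 | 0.5 SD | 28% | 29% | 34% | 47% |
| 20 | 0.8 SD | 69% | 72% | 80% | 93% |

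**Recall overlap.** Pre-injection share of the window = (28 − day of visit) / 28. At day 14 this is 14/28 = 50%; at week 12 (day 84) it is none. If each recalled day counts equally and the effect is constant from injection onward (both assumptions), the estimated difference is the true one times the post-injection share. With 16 per arm and a true 0.8 SD:

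| Visit day | Pre-injection days | Estimated difference | Unadjusted power, r = 0.3 / 0.5 / 0.7 |
|---|---|---|---|
| 11 | 17 of 28 (61%) | 0.8 × 11/28 = 0.31 SD | 18% / 17% / 16% |
| 14 | 14 of 28 (50%) | 0.8 × 14/28 = 0.40 SD | 27% / 24% / 22% |
| 17 | 11 of 28 (39%) | 0.8 × 17/28 = 0.49 SD | 37% / 33% / 30% |

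Here r is the correlation between the pre- and post-injection states.

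**ANCOVA at week 2.** If the baseline form equals the pre-injection state, the residual SD at day 14 is ½√(1 − r²). The ratio 0.4 / [½√(1 − r²)] equals 0.8 / √(1 − r²), so power matches week 12: about 62%, 70% and 85%. That is a ceiling. The Protocol ties the stop of overactive-bladder medication to the diary ("they will be required to stop at least 3 weeks prior to undergoing the baseline 3 day voiding diary"), not to the questionnaire, so the baseline form may describe a different state. If the two states correlate at 0.7 to 0.9, ANCOVA power is about 34–55%, or 40–65% if baseline also keeps its own correlation with the post-injection state. In every case the estimate stays at 0.4 SD: adjustment sharpens the comparison but does not undo the dilution.

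**The case against.** The strongest reply is that this is advice on efficiency for a secondary endpoint. The unadjusted comparison is unbiased, the gain depends on an assumed correlation, and at r = 0.3 it is under 3 points. If the arms, which receive the same total dose, differ by only 0.3 SD, power moves from 13% to between 14% and 20%. All of that stands. It limits the benefit but gives no reason to discard a measurement already taken.

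Next, the documents plan no equivalence claim from the week-2 form, and efficacy is judged on the week-12 diary. This also stands, so the risk depends on how week 2 is reported. Nor would a null week-12 OABq-SF result show equality, given 28–59% unadjusted power. Week 2 differs in that its estimate is diluted as well as imprecise.

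The halving rests on equal weighting of days and a constant effect. If patients weight recent days more, the dilution is smaller; if the effect builds up over days, it is larger. That pre-injection days fall inside the question at day 14 does not depend on either assumption.

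Finally, PGIC also lacks a named visit, and ANCOVA cannot help there because it has no baseline. The simulations used normal scores only. Both are fair limits on what this point covers. A paired test on independent arms is a separate error, and this point does not rest on it.

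**Conclusion.** The concern holds. The plan names no visit for the OABq-SF comparison and does not use the baseline score it collects, and neither document acknowledges the recall overlap at week 2.

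For a true 0.8 SD difference with 16 per arm, omitting baseline costs about 3 to 26 points of week-12 power across correlations of 0.3 to 0.7. At 0.5 SD the cost is about 1 to 19 points. At a day-14 visit, half the recall window precedes injection, and under equal weighting the week-2 difference is halved.

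The textual facts are firm; the power figures rest on assumed effects, correlations and recall weighting. The primary NPRS analysis is unaffected.

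**What to change.** - Compare OABq-SF bother and HRQoL between arms by ANCOVA with the matching baseline score as covariate. Make this the main analysis in place of the paired or unadjusted t-test.
- Report both scores at both visits, with week 12 as the main time point and week 2 as supporting.
- With the week-2 result, give the observed days from injection to completion of the form. State that recall includes pre-injection days, so the arm difference is attenuated: by about half at day 14 under equal weighting, more if earlier, less if later. Add that a null result is not evidence of equal efficacy.
- If unadjusted results have been seen, report them as well, and label both the ANCOVA and the choice of week 12 as post hoc. The SAP is written in the past tense, so this may well apply.

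The cost is SAP and reporting wording plus a re-run on data already collected, with one degree of freedom spent on the covariate. No form or visit changes. The gain may be small if the correlation is low, and at week 2 it may fall well short of the ceiling.
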